1. PURPOSE OF THE STUDY

a. Brief Summary

The purpose of the research is to assess the effectiveness of a medication called tranexamic acid (TXA) when given intraoperatively to reduce bleeding postoperatively after sinonasal surgery (e.g. septoplasty, endoscopic sinus surgery). This medication has already been shown to decrease blood loss during surgery, but the implications for bleeding after surgery are unclear. Any impact on postoperative bleeding from the nose will be assessed over the first 7 days following surgery leading up to the first postoperative clinic visit.

b. Objectives

We hope to learn whether use of the tranexamic acid (TXA) lowers the amount of bleeding after surgery as well as the need for repeat evaluation and additional intervention including nasal packing, cautery, and return trips to the OR. If the medication proves effective in doing so, this knowledge will help provide a rationale for sinus surgeons to routinely use this medication intraoperatively to reduce postoperative bleeding, thereby improving the patient experience and reducing use of hospital resources, both in terms of physical and human capital.

c. Rationale for Research in Humans

This study evaluates the clinical effect of tranexamic acid (TXA) on bleeding followed sinonasal surgery. As a clinical study, it necessarily involves the use of human subjects to assess the impact. The study will also evaluate the patient experience and the impression that patients have of their own bleeding following these procedures.

2. STUDY PROCEDURES

a. Procedures

After a patient in the outpatient clinic has been recommended for and agreed to sinonasal surgery (e.g. septoplasty, turbinate reduction, endoscopic sinus surgery), they will then be eligible for screening for the study. Patients will only be informed of the existence of the

study in a clinical context if they meet the screening requirements. Screening may occur either at the preoperative visit that is part of the standard of care, or on the morning of surgery during the surgical consent process if the patient decided to schedule surgery remotely without a preoperative visit. For any patients who have their pre-op visit via telehealth instead of in-person, it will still be brought up in the clinical context of that pre-operative visit. If a patient is interested, the patient will receive more information regarding the study details, and if the patient wishes to participate after a full informed consent process, written consent will be obtained. Patients will need to be able to provide voluntary consent; those who cannot will be excluded. Patients will be excluded if they are under 18 years of age, are pregnant or may become pregnant by time of surgery, are prisoners, are international participants, are unable to provide consent, or are non-English speaking. Patients will also be excluded if they have known pro-thrombotic clotting disorders. Other patients that are not specifically targeted but will not necessarily be excluded include employees and students, as long as they are able to provide voluntary consent. Once a patient has had all questions answered and has voluntarily enrolled in the study, the patient will be provided with a bleeding diary template to record the postoperative experience which include VAS evaluation postoperative bleeding and number of gauze changes per day. They will use this diary template daily postoperatively. Patients will be randomized to receive either the study medication (TXA with saline infusion) or not (saline infusion alone). The surgeon will be blinded to this selection. The anesthesiologist will not be blinded. However, the patient's participation in the study will be announced during the surgical time out, and it will be announced that the attending surgeon is blinded to the patient's participation. The patient will undergo general anesthesia and undergo their sinonasal surgery as routine. The study intervention will occur 15 minutes before completion of the surgery. At this time, a 1,000 mg IV dose of tranexamic acid will be added to the saline infusion by the anesthesiologist for patients randomized to the intervention. Patients randomized to placebo will continue to receive their routine infusion of normal saline, which is administered throughout surgery. The anesthesiologist will be asked only to state 'study medication administered' at the time of administration, whether the infusion consists of saline alone or with the addition of TXA. This will be the only way in which the two study arms differ. To standardize patient management, packing materials (e.g. nasopore, surgical, Floseal) will not be used at the end of a surgery. However, if a patient experiencing clinically concerning bleeding at the termination of surgery that requires use of these materials (or the clinically indicated use of a dose of TXA), they will be unblinded, removed from the protocol, and managed accordingly. Patient safety will always take priority. After reversal of anesthesia and extubation, patients will be transported to recovery as per standard of care. They will be discharged home when meeting routine post-anesthesia criteria (tolerating oral intake, control of nausea, control of pain, etc). After discharge home and through the following week leading up to their postoperative visit, all patients will fill out the diary template outlined above to characterize their daily postoperative bleeding. Patients will then follow up for their first postoperative clinic visit one week after surgery which is the standard of care. They will turn in their postoperative bleeding diary entries at this time. Their active obligation at this point is over, but they will always have the right to have their data removed from analysis if they wish to withdraw. They will not be contacted for research purposes after this point in regards to this specific study, but will continue to follow up clinically as per standard of care. They will have no clinic visits exclusively for

research purposes; the only visits will be part of the standard of care. Surgical residents will maintain a list of study patients on whom they are called to evaluate for postoperative bleeding in the recovery unit. They will be blinded to whether the patient received the study medication or placebo. Records (i.e. via STARR) will be queried to determine the frequency with which patients in each group call the clinic or answering service with bleeding- related concerns. Records of further intervention (nasal packing, cautery, return to OR) will also be gathered. These outcomes will be used to determine the difference between groups. Patients will have received the standard of care for postoperative epistaxis in all these scenarios, identical to patients who are not enrolled in the study. The primary outcome is the patient-reported VAS bleeding score after surgery. This methodology has been used by other published work to assess the impact of agents used at the end of procedures to reduce the rate of postoperative bleeding after sinonal surgery (<https://journals.sagepub.com/doi/10.1016/j.otohns.2009.06.078>). Using their results as a reference, we may expect that the VAS score on postoperative day one may drop from a 4 to a 2. Assuming an SD of 1.6-1.8 for the purpose of estimations, we would need 24-28 total cases to detect the effect size of 2 in VAS if using 1:1 ratio with 80% power. The secondary outcome is the frequency with which the service is requested to evaluate patients in the recovery unit for postoperative bleeding concerns after sinonal surgeries. Anecdotal feedback from the resident service suggests that they are requested to evaluate roughly 30% of these patients. With the hypothesis that the TXA could reduce the frequency by roughly half to 15%, we will require 118 patients in each group (total N=236) to achieve 80% power to detect a difference between the two group proportions of 15% (with 30% in placebo, 15% in TXA group). This estimate uses two sided Z-test while assuming type I error=0.05.

b. Procedure Risks

These procedures involve the delivery of routine standard of care in all facets of sinonal surgery with the addition of a single medication intervention to be delivered intraoperatively while under the direct care and supervision of the anesthesiology service. Any unexpected hemodynamic or clinical side effects can therefore be immediately assessed and addressed. The planned medication dose is based on previous studies and has been extremely well tolerated during studies evaluating its use in endoscopic sinus surgery to assess the effect on intraoperative bleeding. Higher doses have been used for other indications including orthopedic surgery, however we plan to utilize this lower dose with a proven safety record.

c. Use of Deception in the Study

N/A

d. Use of Audio and Video Recordings

N/A

e. Alternative Procedures or Courses of Treatment

The alternative is not to participate and to receive the routine standard of care with no change in risks. This involves observation after surgery with traditional management of epistaxis if it occurs (oxymetazoline nasal spray and pressure, Floseal hemostatic matrix,

formal nasal packing as required). These will still all be available for patients, as their utilization is one of the endpoints of the study. No care or alternative medications are being withheld in order to participate in this study. This is an additional intervention to the routine standard of care. All patients will continue to be treated as clinically indicated.

f. Will it be possible to continue the more (most) appropriate therapy for the participant(s) after the conclusion of the study?

Patients will receive the appropriate standard of care both during and after the conclusion of the study. Nothing will change in regards to their normal clinical management by participating in the study.

g. Study Endpoint(s)

Patients data will be gathered for one week postoperatively and their direct participation will end at the first clinical visit one week after surgery (their data will still be analyzed after that time). The primary endpoint is the patient VAS assessment of postoperative bleeding over the first week, and the patient report of gauze usage over the first week. Secondary endpoints to be evaluated will include the proportion of patient in recovery on whom the nurses contact the on-call resident for assessment with postoperative bleeding, the need for interventions to address postoperative bleeding (cautery, nasal packing, return to OR), and frequency of patient calls to clinic after discharge home with bleeding concerns. If during interim data analysis a significant difference in postoperative bleeding is noted without an increase in adverse events, discussion could be had with the IRB over developing a new standard of care, however we would anticipate continuing with the standard of care through the end of the study.

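### The control arm gets no matching addition to its infusion and the masking described is only verbal, so the surgeon's blinding is not secured before a judgement that can remove a randomized patient

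*Combined protocol and SAP*

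**What the plan says.** All of the procedure is in section 2.a (Procedures) of the combined protocol and SAP.

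- **Who is masked:** "The surgeon will be blinded to this selection. The anesthesiologist will not be blinded".
- **When:** "The study intervention will occur 15 minutes before completion of the surgery".
- **TXA arm:** "At this time, a 1,000 mg IV dose of tranexamic acid will be added to the saline infusion by the anesthesiologist".
- **Control arm:** "Patients randomized to placebo will continue to receive their routine infusion of normal saline, which is administered throughout surgery".
- **Spoken masking:** "The anesthesiologist will be asked only to state 'study medication administered' at the time of administration", and this applies "whether the infusion consists of saline alone or with the addition of TXA". At the time-out it is also announced that the attending surgeon is blinded.
- **Stated contrast between arms:** "This will be the only way in which the two study arms differ".
- **What follows at the end of surgery:** packing materials are not to be used, but "if a patient experiencing clinically concerning bleeding at the termination of surgery that requires use of these materials", or a clinically indicated dose of TXA, the patient is unblinded and taken out of the protocol.

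The same section says that the residents called to the recovery unit are blinded. Section 2.g says that the recovery outcome arises when nurses contact the on-call resident. No statement is made about whether those nurses are blinded.

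**The concern.** The control is called placebo, but the procedure gives it no placebo act. One arm has something added to its infusion and the other has nothing added. A common spoken phrase masks what is heard, not what is done, and it also marks the moment at which a difference could be noticed.

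The timing makes this important. The addition falls while surgery is still in progress, shortly before a subjective judgement about bleeding that can take a randomized patient out of the trial. If someone involved in that judgement knows the arm, removals could differ between arms for reasons unrelated to bleeding. The patients who remain would then no longer be a randomized comparison. Knowledge of the arm could also travel with the patient to recovery staff, whose calls generate the outcome behind the planned N.

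**Working it through.** **1. The two arms side by side**

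| Step | TXA arm | Control arm |
|---|---|---|
| 15 minutes before completion | 1,000 mg added to the saline | Existing saline continues |
| Person acting | Anesthesiologist, unblinded | No act described |
| Spoken phrase | Yes | Yes, the same |
| Dummy addition, common label, concealed preparation | Not described | Not described |

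The spoken phrase is matched across arms. The physical act is not.

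**2. The plan's own sample size**

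Inputs from section 2.a: 30% vs 15%, two-sided Z-test, type I error 0.05, power 80%. With unpooled variance:

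n = [0.30 × 0.70 + 0.15 × 0.85] × (1.960 + 0.842)² / 0.15² = 0.3375 × 7.849 / 0.0225 = 117.7, so 118 per group and 236 in total.

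This reproduces the stated figure. The primary VAS sizing (difference 2, SD 1.6 to 1.8, two-sample t-test) also reproduces, at 24 and 28 in total. Neither figure is disputed, and a matching saline addition changes neither.

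**3. What arm-dependent removal could do**

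The documents give no removal rates, so this is an illustration on assumed inputs. Take 125 per arm (half of the roughly 250 in section 8.a). Suppose every removed patient would otherwise have led to a recovery-unit evaluation. That is the extreme case.

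With removal fraction r in an arm whose true evaluation rate is p, the rate among those left is p′ = (p − r)/(1 − r), on 125 × (1 − r) patients. The two-sided Z-test has standardized difference d = (p′c − p′t)/SE. The rejection probability is Φ(d − 1.96) + Φ(−d − 1.96).

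Worked case: no true effect (p = 0.30 in both arms), removal of 5% of controls and 10% of TXA patients.
- p′c = 0.25/0.95 = 0.263 on 118.75 patients; p′t = 0.20/0.90 = 0.222 on 112.5.
- SE = √(0.263 × 0.737/118.75 + 0.222 × 0.778/112.5) = 0.0563.
- d = 0.0409/0.0563 = 0.73.
- Rejection probability = Φ(−1.23) + Φ(−2.69) = 0.11.

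| Removed, control / TXA | Type I error (30% in both arms) | Power (30% vs 15%) |
|---|---|---|
| 0% / 0% | 0.05 | 0.82 |
| 5% / 5% | 0.05 | 0.89 |
| 5% / 10% | 0.11 | 0.995 |
| 2% / 10% | 0.20 | 0.999 |
| 10% / 5% | 0.11 | 0.68 |
| 10% / 2% | 0.20 | 0.44 |

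The distortion can go either way. Excess removal in the TXA arm flatters TXA. Excess removal of controls hides a real effect. Under no true effect, equal removal does no harm to the type I error; it is the imbalance that matters.

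**The case against.** The strongest reply is that the protocol says the surgeon is blinded, and that nothing in it shows otherwise. A reader might infer that the surgeon can watch the drug being drawn up and injected into a bag. The documents do not support that. They describe no line of sight, place of preparation, bag, syringe or volume. Nor do they name the surgeon as the person who judges bleeding at the end of surgery, although that is a natural reading. Any count of cases with an unblinded surgeon would rest on a noticing rate that the documents do not give.

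A reader might also infer that both main outcomes would be biased. That goes too far. The VAS is completed by the patient, who is under general anesthesia at dosing. The residents are stated to be blinded, and the surgeon rates neither outcome. Direct bias of the VAS is the weaker route, though removals still decide whose diary is analyzed.

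Finally, removal after randomization could distort the comparison even with perfect blinding, if TXA already affects bleeding by the end of surgery. That is correct, and it is a separate problem.

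All of this limits the size of the point. What stands is that stating that the surgeon is blinded sets an aim, and the procedure as written matches the words spoken in the two arms but not the act.

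**Conclusion.** The point holds as a gap in how blinding is secured, not as a finding that blinding fails. The control procedure leaves an unmatched act shortly before a subjective judgement that can remove a randomized patient, and only spoken measures cover it. Arm knowledge could make removals differ by arm, or could reach recovery nurses, for whom no blinding is stated. Either could bias the recovery-unit outcome.

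The size cannot be derived from the documents. The type I errors of about 0.11 and 0.20 rest on assumed, unequal removal rates and on the extreme assumption that every removed patient would have been evaluated. They show what is possible and are not a forecast. The correction is cheap enough to be worth making without knowing the size.

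**What to change.** In section 2.a, replace the instruction that controls simply carry on with their saline. Instead, the anesthesiologist makes a matching addition of plain saline, equal in volume to the TXA addition, at the same time point. In both arms the addition is prepared out of the surgical team's sight, carries the same 'study medication' label, and is followed by the same spoken phrase. Add that end-of-surgery removals will be reported by arm, with the reason for each.

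**Cost:** one saline syringe and label per control patient, about a minute of the already unblinded anesthesiologist's time, and a short amendment. The sample size does not change and no extra staff should be needed.

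**Limit:** this protects blinding up to the end-of-surgery judgement. It does not cure the removal of patients after randomization, which needs to be handled separately.

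### Patients who bleed at the end of surgery are removed after randomisation and dosing, and nothing keeps them in follow-up or in an as-randomised analysis

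*Combined protocol and SAP*

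**What the plan says.** All of the following is in section 2.a (Procedures) unless noted.

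- Patients are randomised to TXA added to saline or to saline alone. On timing: "The study intervention will occur 15 minutes before completion of the surgery".
- Packing materials are not used at the end of surgery, so that management is the same for everyone. The exception reads: "if a patient experiencing clinically concerning bleeding at the termination of surgery that requires use of these materials", or a clinically indicated dose of TXA, in which case "they will be unblinded, removed from the protocol, and managed accordingly".
- After discharge, "all patients will fill out the diary template outlined above to characterize their daily postoperative bleeding". Removed patients are not mentioned.
- The only explicit rule on taking data out of the analysis concerns the patient's own choice: "they will always have the right to have their data removed from analysis if they wish to withdraw".
- For the recovery-unit outcome, "Surgical residents will maintain a list of study patients on whom they are called to evaluate for postoperative bleeding in the recovery unit". For interventions, "Records of further intervention (nasal packing, cautery, return to OR) will also be gathered".
- Section 1.a gives the reason to expect an effect of the drug on bleeding: "This medication has already been shown to decrease blood loss during surgery, but the implications for bleeding after surgery are unclear".
- Section 2.e describes use of measures such as Floseal and formal packing as an endpoint, and section 2.g lists nasal packing among the secondary endpoints.

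The document defines no analysis population, no as-randomised or intention-to-treat analysis, and no data collection after removal.

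**The concern.** In the planned sequence, removal follows both randomisation and dosing, and it is triggered by bleeding. If TXA changes bleeding at the end of surgery, the arms will lose different numbers or kinds of patients, and those who remain are no longer the groups that were randomised. The patients lost are also close to the events being counted: Floseal is named both among the materials that trigger removal (2.a) and among the measures whose use is an endpoint (2.e).

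The VAS, recovery-unit and intervention comparisons are all exposed. Calls and interventions come from records and could probably be recovered later. VAS scores and gauze counts come from a diary kept in the first week. If it is not collected then, the primary outcome is lost for these patients.

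**Working it through.** **Inputs from the plan.** Section 2.a: 30% vs 15% recovery-unit evaluations, two-sided Z-test, alpha 0.05, 80% power, 118 per group; VAS falling from 4 to 2 with SD 1.6-1.8. Section 8.a: about 250 patients, so 125 per arm.

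**The plan's own figure.** The unpooled formula gives n = (1.960 + 0.842)² × (0.30×0.70 + 0.15×0.85) / 0.15² = 117.7, rounded up to 118. The stated size reproduces and is not in dispute.

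**Assumptions, not in the plan.** r is the share of an arm that is removed, and f is the share of removed patients who would have been recovery-unit events. Removal is written placebo/TXA. The VAS is taken as 0-10.

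**Recovery-unit outcome if removed patients are excluded.** Retained event rate = (p − f·r)/(1 − r), on N(1 − r) patients per arm, tested with the unpooled Z.

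Worked case with no true effect (30% in both arms), N = 125, removal 10%/5%, f = 1:
- Placebo: (0.30 − 0.10)/0.90 = 22.2% of 112.5. TXA: (0.30 − 0.05)/0.95 = 26.3% of 118.75.
- Difference −4.1 points; SE = √(0.222×0.778/112.5 + 0.263×0.737/118.75) = 0.0563; ratio −0.73.
- False positives: 10.9% against TXA and 0.4% in its favour, 11.2% in total before rounding. The mirror split, 5%/10%, gives 10.9% in favour of TXA.

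| Removal | False positives, f = 1 | f = 0.5 | f = 0.3 |
|---|---|---|---|
| 2%/1% | 5.2% | 5.0% | 5.0% |
| 5%/2.5% | 6.2% | 5.1% | 5.0% |
| 10%/5% | 11.2% | 5.4% | 5.0% |

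Simulation of 400,000 trials at f = 1 gives 5.4%, 6.5% and 11.6%, against 5.2% with no removal.

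Power for 30% vs 15% at 118 per arm is 80% without removal. At 10%/5% and f = 1, the retained rates are (0.30 − 0.10)/0.90 = 22.2% and (0.15 − 0.05)/0.95 = 10.5%, a difference of 11.7 points.

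| Removal | Power, f = 1 | f = 0.5 | f = 0.3 |
|---|---|---|---|
| 2%/1% | 78% | 80% | 80% |
| 5%/2.5% | 74% | 79% | 81% |
| 10%/5% | 65% | 77% | 81% |

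**VAS, no true effect, mean 4 in both arms, whole-arm SD held at 1.6 or 1.8, 125(1 − r) per arm.**
- Removed patients average 6: the retained mean is (4 − 6r)/(1 − r), so at 10%/5% it is 3.78 vs 3.89. False positives are 5.1%, 5.7-5.8% and 8-9% across the three removal scenarios.
- Removed patients are exactly the worst tail of a normal distribution (upper bound): 5.4%, 7.0% and 11.7%. The shift at 10%/5% is −0.138 (SD 1.6) or −0.156 (SD 1.8).
- Power: the planned difference of 2.0 becomes at worst 2.0 − 0.156 = 1.84. With SD 1.8 and 112.5 in each arm, the SE is √(2×1.8²/112.5) = 0.24, so the difference is still more than seven standard errors.

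**If they are kept and analysed as randomised.** Rescue can lower their event rate to g, so the arm rate becomes p − r(f − g). At 10%/5% and 118 per arm:
- f = 1, g = 0.5: 0.30 − 0.10×0.5 = 25.0% and 0.15 − 0.05×0.5 = 12.5%. The difference is 12.5 points with 70% power, against 11.7 points and 65% with exclusion.
- f = 0.5, g = 0: again 25.0% vs 12.5%, with 70% power, against 14.6 points and 77% with exclusion.

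**The case against.** The strongest reply is that the plan never says these patients leave follow-up or analysis. The clause directly follows the rule that standardises packing and ends by speaking of management, so it may release the patient only from that rule and from blinding. The diary sentence covers all patients without exception. The only stated reason for taking data out of the analysis is voluntary withdrawal, and section 2.e treats use of packing as an endpoint. This is a fair reading and cannot be excluded. But it is not the natural one, and none of these texts mentions removed patients or places them in an analysis. Section 2.e also concerns care after surgery. A sentence that two teams could apply differently to the worst bleeders needs settling either way.

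The size is also assumed. The 11.2% figure needs 10% removal, a twofold difference between arms and every removed patient being an event; milder cases are close to nothing, and equal removal with the same case mix gives no bias under the null. All of that stands.

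It can also be said that if TXA works, more placebo patients are removed and the bias runs against TXA. That is plausible, but the sign depends on the arm split and on whether removed patients would have had more or fewer events than the rest, and the plan fixes neither.

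Finally, retained patients will have been unblinded and rescued. This can affect a self-reported score and can dilute the comparison. That stands as a cost of the remedy.

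**Conclusion.** The concern holds and should be fixed. On its natural reading the clause is an outcome-related exclusion after randomisation, and nothing in the document corrects it. The milder reading is possible, so confidence is medium.

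The size is unknown because no removal rate is stated. In the scenarios examined, the false-positive rate for the recovery-unit outcome runs from 5.0% to 11.2%, and power from 65% to about 80%. For the VAS the false-positive rate runs from 5.1% to 11.7%, and power is not threatened at about 250 patients. The upper ends rest on 10%/5% removal (or its mirror, for false positives) and on the extreme assumption about who is removed. The case for change is validity, not power: keeping these patients can raise or lower power. The 14 patients above 236 (250 − 236) replace lost numbers, not patients lost selectively.

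**What to change.** Leave clinical handling and unblinding as they are. Replace the removal wording with a sentence such as: *the patient remains in study follow-up (diary, recovery-unit, intervention and call data) and is analysed in the arm to which he or she was randomised*. If the sponsor meant only release from the no-packing rule, the same sentence says so.

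In addition:
- Report the number of such patients and the reason by arm, and whether each learned the allocation before completing the diary.
- State whether end-of-surgery packing counts in the intervention endpoint, so that sections 2.a, 2.e and 2.g agree.
- Pre-specify two sensitivity analyses: one excluding these patients, which reproduces the natural reading of the current text; and one giving them the worst VAS rank and counting them as recovery-unit events. The second needs a rank-based test and carries an end-of-surgery event into a one-week outcome, so it should not be the main analysis.

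The cost is one sentence, matching consent wording if needed (the consent pages were not available to check), the two analyses, and about 4 to 19 extra diaries (125 × 0.03 = 3.75 to 125 × 0.15 = 18.75). These patients already hold the diary and attend the one-week visit as standard of care. The downsides to accept are possible reporting bias after unblinding and dilution by rescue, including crossover when a placebo patient receives clinical TXA.

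### Patients who need packing or clinical TXA at the end of surgery are removed after randomisation and dosing, and nothing keeps them in follow-up or analysis, which can bias the bleeding comparisons

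*Combined protocol and SAP*

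**What the plan says.** Section 2.a (Procedures) sets the order of events. Patients are randomised to TXA or saline alone, and "The study intervention will occur 15 minutes before completion of the surgery". Packing materials are not used routinely at closure. The exception is clinically concerning "bleeding at the termination of surgery that requires use of these materials (or the clinically indicated use of a dose of TXA"). For those patients the instruction is that "they will be unblinded, removed from the protocol, and managed accordingly".

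A little later, 2.a says that after discharge "all patients will fill out the diary template outlined above to characterize their daily postoperative bleeding". It does not say whether this includes patients already removed.

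Section 2.g (Study Endpoints) states: "The primary endpoint is the patient VAS assessment of postoperative bleeding over the first week", and adds gauze use over the same week. The secondary endpoints include the proportion of recovery patients about whom "the nurses contact the on-call resident for assessment with postoperative bleeding", later interventions (cautery, packing, return to the operating room), and calls to the clinic. Section 2.e also describes use of haemostatic matrix and packing as an endpoint.

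The document has no definition of an analysis population, no as-randomised analysis, no rule for counting removed patients, and no expected removal rate.

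**The concern.** Removal is decided after allocation and after dosing, and the reason for it is bleeding. Section 1.a says of TXA: "This medication has already been shown to decrease blood loss during surgery". On the plan's own premise, then, the share removed could differ between arms. Even equal shares would not guarantee that the patients left in each arm are comparable, because different kinds of patients may be removed from each.

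The trial asks whether TXA reduces bleeding and further intervention after surgery. A rule that drops patients already bleeding enough at closure to need treatment takes out people who bear directly on that question. It also takes closure packing out of an endpoint family that includes packing. If the diary stops at removal, those VAS and gauze data cannot be rebuilt later.

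**Working it through.** **Inputs from section 2.a.** Recovery-call rates 30% (placebo) and 15% (TXA), 118 per group, two-sided Z-test, alpha 0.05, 80% power. Day-one VAS 4 v 2, SD 1.6–1.8, 24–28 patients in total.

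**The plan's own figures.** Unpooled Z formula: n = (1.960 + 0.842)² × (0.30×0.70 + 0.15×0.85) / 0.15² = 117.7, so 118 per group, as stated. The two-sample t-test for VAS needs 11.1 per arm at SD 1.6 and 13.7 at SD 1.8, so 24 and 28 in total, also as stated. The sample sizes are not in dispute. With the pooled test used below, 118 per group gives 79% power, which is the baseline for comparison.

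**Assumed input.** The document gives no removal rate. The main illustration takes 10% of placebo and 5% of TXA patients; smaller rates follow.

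**Recovery calls.** Let r be the share of an arm removed and f the share of removed patients who would have been recovery calls. The observed rate is (p − r·f)/(1 − r), with 118 × 0.90 ≈ 106 and 118 × 0.95 ≈ 112 patients left.

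| f | Placebo | TXA | Difference | Power |
|---|---|---|---|---|
| 0 | 0.30/0.90 = 33.3% | 0.15/0.95 = 15.8% | 17.5 points | 86% |
| 0.5 | 0.25/0.90 = 27.8% | 0.125/0.95 = 13.2% | 14.6 points | 77% |
| 1 | 0.20/0.90 = 22.2% | 0.10/0.95 = 10.5% | 11.7 points | 65% |

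The plan is 15 points and 79%. Smaller removal rates move it less. At 5% v 2.5%, f = 0.5 gives 14.8 points and 78% power, and f = 1 gives 13.5 points and 73%. At 2% v 1% with f = 1, the result is 14.4 points and 77%.

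**If TXA has no effect on calls (30% in both arms), 10% v 5% removed.**
- f = 1: 0.20/0.90 = 22.2% v 0.25/0.95 = 26.3%, a spurious 4.1 points against TXA. Two-sided rejection is about 11% instead of 5%.
- f = 0.5: 0.25/0.90 = 27.8% v 0.275/0.95 = 28.9%, about 1.2 points. Rejection is about 5.4%.

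**VAS.** Take the worst case: scores are normal and the removed patients are exactly the highest scorers. The mean of those left is mu − SD × phi(z)/(1 − r), where z is the (1 − r) normal quantile. For r = 10%, phi(z)/(1 − r) = 0.1755/0.90 = 0.195. For r = 5%, it is 0.1031/0.95 = 0.109.
- SD 1.6: 4 − 0.31 = 3.69 v 2 − 0.17 = 1.83, difference 1.86.
- SD 1.8: 4 − 0.35 = 3.65 v 2 − 0.20 = 1.80, difference 1.84 before rounding.

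The loss is 0.14–0.16 against a planned 2.0. At 5% v 2.5% removed it is 0.08–0.09. Equal removal leaves the VAS difference at 2.0 under this model.

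**The case against.** **Removal from the protocol is not literally exclusion from analysis.** Section 2.a uses different words for data withdrawal at a patient's request, and its diary sentence refers to all patients. This stands as a limit: a reader might infer that the plan expressly excludes these patients from analysis, and it does not. Exclusion is still the natural reading, because nothing says that they are followed or analysed. If the sponsor intends otherwise, the text has to say so.

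**The larger figures need extreme assumptions.** This also stands. A fall in power to 65% requires every removed patient to have been a recovery call. These patients would already have had packing or rescue TXA, so that is unlikely. Midway, the effect is small.

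**Differential removal is weakly supported.** The statement in section 1.a concerns blood loss during surgery. The dose here comes 15 minutes before the end, and the document reports nothing on closure packing. A reader might infer that the rule must favour TXA, or must penalise it; neither can be shown. Blinding of the surgeon limits deliberate selection, but not selection that works through the drug's effect.

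**Some data could be retrieved.** Clinic calls and later interventions come from records, so it would be wrong to say that all outcome data are lost. What is at risk is the diary, and possibly the residents' list of study patients.

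**Automatic unblinding might look like a second fault.** It is not a defect in the current plan: unblinding a removed patient does not affect results from which that patient is absent, and of the residents the plan says "They will be blinded to whether the patient received the study medication or placebo". It matters only once these patients are retained.

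**Conclusion.** The concern holds in a limited form. Followed as written, section 2.a creates an outcome-related removal after randomisation and dosing, and nothing elsewhere restores these patients to follow-up or to an as-randomised comparison. That can bias the VAS, gauze, recovery-call and intervention results. It does not show that they will be biased materially or in a known direction.

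At the assumed 10% v 5%, the recovery-call difference lies between 17.5 and 11.7 points, against 15 planned. The primary VAS comparison is robust at the planned effect of 2; a shift of up to 0.16 would matter more if the true effect were small. The change should be made because it is cheap and because diary data not collected cannot be recovered. Confidence is medium: the wording of the rule is clear, but exclusion from analysis is inferred and the removal rate is unknown.

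**What to change.** In section 2.a, leave rescue treatment as it is and replace removal with continued participation:

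- Continue the diary, the one-week visit and record follow-up for these patients, and keep them on the residents' list.
- Analyse them in their randomised arm, recording closure packing or rescue TXA as an intercurrent event.
- State that closure packing counts as an event in the packing/intervention endpoint.
- Report the number of such patients per arm.
- Add a sensitivity analysis that excludes them.

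As a note to this change only: once these patients are retained, break the code only when knowing the arm would change care (for example before rescue TXA), tell only those who need to know, and log it. This keeps the patient's VAS and the residents' assessments blinded. The anesthesiologist already knows the allocation, so safety is not affected.

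The cost is a few sentences, a short code-break log and one extra analysis; the diary and visit already exist. The downside is that packing or rescue TXA in retained patients dilutes the contrast somewhat, and packing may itself alter VAS and gauze counts. The sensitivity analysis shows how far the result depends on these patients.
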